The INSPIRE-ASP Trial (INtelligent Stewardship Prompts to Improve Real-time Empiric Antibiotic Selection for Patients) for Abdominal (ABD) Infections Protocol

NCT:05423743

6/24/2020

Brief Overview

The **INSPIRE-ASP Trial (INtelligent Stewardship Prompts to Improve Real-time Empiric Antibiotic Selection for Patients) for Abdominal (ABD) Infections** is a cluster-randomized trial of 92 hospital randomized units (102 individual hospitals) to improve physicians' choice of antibiotics for patients hospitalized with ABD infections by reducing the unnecessary use of extended-spectrum antibiotics. This trial provides prescribers in half the hospitals with prescribing advice based on the probability that a patient is infected with antibiotic resistant bacteria. Provision of unnecessary extended-spectrum antibiotics carry risks, and the goal of this trial is to limit their use to situations in which the patient is likely to require them, while maintaining excellent patient outcomes.

We hypothesize that providing clinicians with individual patient risk estimates for antibiotic-resistant infections will reduce the overuse of empiric extended-spectrum antibiotics among patients hospitalized for ABD infections. To do this, we will use patient information in the electronic health record plus local hospital laboratory data on antibiotic resistance in ABD cultures to develop an automated smart tool that provides the likelihood that a patient needs extended-spectrum antibiotics. 102 hospitals were randomized into 92 hospital units, into either routine care (46 hospital units) or to the intervention arm (46 hospital units) receiving the INSPIRE Stewardship Bundle which includes CPOE smart prompts, clinician feedback reports, and activities to support CPOE adoption (e.g., education and modifications of CPOE workflows as needed). In half of these hospitals, physicians will be prompted to use standard-spectrum antibiotics when the risk of antibiotic-resistant infection is low. This 12-month intervention will evaluate approximately 99,000 patients with ABD infections.

Protocol Summary

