This protocol provides detailed instructions for the conduct of the INSPIRE-ASP Trial (INtelligent Stewardship Prompts to Improve Real-time Empiric Antibiotic Selection for Patients) for Abdominal (ABD) Infections. This trial is a 92 hospital unit (102 individual hospitals), 99,000 patient cluster-randomized trial to improve physicians' choice of antibiotics for hospitalized patients by reducing the unnecessary use of extended-spectrum antibiotics while maintaining excellent patient outcomes. This trial will be conducted in the HCA Healthcare system, which provides 5% of acute care services in the United States.

Hospitals will be recruited through usual HCA Healthcare communication channels and randomized into a two-arm trial involving routine care or routine care plus a stewardship bundle that includes real-time personalized risk calculator for whether a patient with ABD infection is infected with an antibiotic-resistant pathogen warranting extended-spectrum antibiotic therapy. This protocol details eligibility criteria for participation, factors accounted for in 1:1 hospital randomization, notification of randomization assignment, and provision of the two arms with arm-specific toolkit information and coaching calls. It also details the process by which centralized IRB approval and reliance agreements will be obtained.

This trial evaluates a quality improvement antibiotic stewardship strategy, the INSPIRE Stewardship Bundle, that includes (1) computerized physician order entry (CPOE) decision support alert that provides physicians with patient-specific risk estimates for having a (ABD) infection due to a multidrug-resistant organism (MDRO) and recommends standard spectrum antibiotics for low risk patients in the first 3 days of hospitalization; (2) clinician feedback reports, and (3) activities to support CPOE adoption (including education and alignment of CPOE workflows). As such, all implementation will be performed through the local infrastructure provided by hospital antibiotic stewardship program leaders who serve as study champions. Participating hospitals in both arms will approve the arm-specific study protocol through usual hospital committees. The routine care arm will participate in regular coaching calls to ensure best practice for national standards of stewardship are taught and encouraged. This arm will also launch trial-specific modifications to the existing antibiotic indication screens.

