Several activities are detailed for the INSPIRE Stewardship Bundle arm. These include pre-launch activities such as participation in coaching calls and an on-site training visit, as well as procedures to locally install corporate MediTech software for the CPOE personalized risk calculator for ABD infection antibiotic indications, including any modifications needed to align the CPOE workflow to support the INSPIRE prompts (e.g., order-based exclusion of ICU patients, order set changes). In addition, the sites receiving the INSPIRE Stewardship Bundle will receive educational materials, participate in monthly coaching calls and every other month check in calls, and receive clinician audit reports to feedback to physicians and hospital leadership about protocol adherence.

As a pragmatic trial, all data will be obtained from the HCA Healthcare centralized clinical data warehouse. Local site champions will not need to collect any outcome data or variables for description or adjustment. This protocol describes how data will be obtained through a data use agreement between HCA Healthcare and Harvard Pilgrim Health Care Institute (data and analytic center for the trial). Data and programmer analysts will access and analyze data on the HCA Healthcare server behind the HCA Healthcare firewall, thus ensuring maximum data protection.

In summary, the INSPIRE Trial for Abdominal (ABD) Infections is a randomized trial of 92 hospital units (102 individual hospitals) and approximately 60,000 patients to improve physicians' choice of antibiotics for patients hospitalized with abdominal infection by reducing the unnecessary use of extended-spectrum antibiotics. This protocol provides the road map for the conduct of the trial to determine if a personalized real-time risk calculator plus audit and feedback can improve judicious use of antibiotics in hospitalized patients.

B. Background Information and Scientific Rationale

B.1. Background Information

National Call for Antibiotic Stewardship in an Era of Antibiotic Resistance

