Abbreviations: **MRSA** - Methicillin Resistant *Staphylococcus aureus*; **VRE** – Vancomycin Resistant *Enterococci*; **ESBL** – Extended Spectrum Beta Lactamase producer; **CRE** – Carbapenem Resistant Enterobacteriaceae

Participating hospitals are randomized to:

- **Arm 1 – Routine Care**
- **Arm 2 – Real-Time Risk Estimation Smart Prompt**

Computerized physician order entry (CPOE) prompt that recommends standard-spectrum

antibiotics in patients admitted for ABD infections who are prescribed extended-spectrum antibiotics and calculated to have low risk (<10%) for an antibiotic resistant infection.

Trial Outcomes

Table 2: Primary and Secondary INSPIRE-ASP Abdominal Infections Trial Outcomes

Outcome	Metric
Primary Trial Outcome	
Total Empiric Extended-Spectrum Antibiotic Days of Therapy (ES-DOT)	The number of different extended-spectrum antibiotics received by the patient each empiric day, summed across the first 3 days of hospitalization. ¹
Secondary Trial Outcomes	
Vancomycin Days of Therapy per Empiric Day	The number of days Vancomycin was received by the patient on the first 3 days of hospitalization. ¹
Total Empiric Antipseudomonal Antibiotic Days of Therapy	The number of different antipseudomonal antibiotics received by the patient each empiric day, summed across the first 3 days of hospitalization. ¹

¹E.g., if a patient is admitted for 2 days, ES-DOT will be calculated across those 2 days; however if a patient is admitted for 4 days, only the first 3 days will be evaluated.

Safety outcomes planned for the primary manuscript are shown in Table 3. Length of stay and days to ICU transfer are evaluated within 14 days of admission since empiric antibiotic selection within the first 3 hospital days is not expected to be the main driver of either outcome beyond this time; evaluation of baseline data also shows that 93% of abdominal patients have length-of-stay equal to or less than 14 days.

Table 3: Other Pre-Specified Outcomes – Trial Safety Outcomes

Safety Trial Outcomes (other pre-specified outcomes)	
ICU Transfer [Safety Outcome]	Days to ICU transfer, between hospital days ≥ 3 and ≤ 14 .
Length-of-stay [Safety Outcome]	Days from hospital admission until discharge or hospital day 14, whichever comes first, where admission day is hospital day 1.

Data Collection Details

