The unit of analysis will be individual admissions. Individual patients can contribute more than one admission. The analytic model will be a generalized linear mixed effects model for differences in differences, with random effects to account for correlation within hospital between period, within hospital within period between patient, and within patient between admission. We plan to use a Poisson model for analysis of outcomes as follows:

$$\log(y_{ijph}) = \beta_0 + \beta_1 A_{ijph} + \beta_2 T_{ijph} + \beta_3 A_{ijph} T_{ijph} + b_{0h} + b_{1h} T_{ijph} + g_j + \log(ed_j)$$

where y_{ijph} is the ES-DOT for patient i for admission j in period p at hospital h , and $A_{ijph} = 1$ if hospital h is in the intervention arm and 0 if not, and $T_{ijph} = 1$ if p is the intervention period and 0 if baseline period. The random effects b_{0h} and b_{1h} allow for different baseline mean admission-level ES-DOT for each hospital and each hospital in the intervention period, respectively. Equivalently, they allow for correlation within hospital at different levels at baseline and at follow-up. The random effect g_j allows each patient to have a different mean ES-DOT. Finally, ed_j is the number of empiric days in the admission. We note that it may not be possible to fit models with the g_j parameter, for various numerical and computational reasons—the most prominent being a relative sparsity of patients with readmissions. If that proves to be the case, we will randomly select one admission per patient and use the model above without that parameter and omitting the j subscript.

The assessment of trial success will be determined by assessing the significance of the arm by period interaction term β_3 , which estimates the log relative rate of the outcome due to being in the intervention arm in the intervention period. The exponentiated parameter estimate for β_3 is the estimated relative rate of ES-DOT per at-risk day due to the intervention, relative to the baseline period. For example, if β_3 had a negative value and a p-value <0.05 , we would conclude that the patient-specific CPOE smart prompts generated a benefit over routine care. Exponentiating the parameter value would provide an estimate of the relative reduction due to the intervention in the expected ES-DOT per at-risk day.

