The primary trial analysis will use an as-randomized unadjusted model with two-tailed significance set at alpha = 0.05. Secondary outcomes will be assessed using an as-randomized unadjusted model and will include adjustment for multiple comparisons with two-tailed significance set at alpha = 0.025 for the two secondary outcomes.

Subsequent analyses of the primary and secondary outcomes will include both as-treated and adjusted models. Adjusted models will account for individual characteristics such as age, gender, comorbidities, and prior history of MDROs as well as hospital characteristics such as hospital antibiotic resistance. We will also account for seasonality. All adjusters will be determined a priori. These analyses will be reported as point estimates with confidence intervals and without p-values. The reason for including these analyses is to provide additional

information related to the trial outcomes for readers to assess the effects of potential confounders. The reason to not include them in a formal multiple comparisons adjustment is because these analyses are non-independent evaluations relative to the as-randomized unadjusted analyses.

Safety Outcomes

Safety outcomes are required because a reduction in ES-DOT might be achieved only by incorrectly withholding ES antibiotics when they were necessary. Each safety outcome will be evaluated for non-inferiority using an as-randomized unadjusted analysis with a one-tailed significance set at alpha = 0.05. For length of stay, the non-inferiority margin is a hazard ratio of 0.98. For days to ICU transfer, the non-inferiority margin is a hazard ratio of 1.1 (fewer days to ICU results in a hazard ratio above 1). Analyses planned for these assessments are proportional hazards models with random effects for each time period, hospital, and admission. These models are sometimes called frailty or shared frailty models. Because these are safety outcomes, we do not intend to make adjustments for multiple comparisons in testing them, further increasing conservatism. As above, it may not be possible to include multiple admissions.

All analyses will be performed using current versions of SAS/STAT and/or R packages lme4 and coxme, unless better packages become available in the meantime.

Further Planned Analyses

We note that there are other pre-specified outcomes intended for exploratory analysis in secondary papers for the INSPIRE ABD trial in Table 5 below.

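### The worked conclusion for a positive primary result credits the CPOE prompts, but the arm comparison estimates the effect of the whole INSPIRE Stewardship Bundle

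*SAP*

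**What the plan says.** **The conclusion attached to the test.** The SAP, under Primary Statistical Analysis, bases trial success on the significance of the arm-by-period interaction β3, "which estimates the log relative rate of the outcome due to being in the intervention arm in the intervention period". It then gives an example: if β3 is negative with p below 0.05, "we would conclude that the patient-specific CPOE smart prompts generated a benefit over routine care". Protocol H.3 has the same example in the same words. The test is set out plainly: "The primary trial analysis will use an as-randomized unadjusted model with two-tailed significance set at alpha = 0.05".

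**Arm 2 in the SAP.** The Background describes the trial as comparing routine care with a smart prompt, and the list of arms labels Arm 2 "Real-Time Risk Estimation Smart Prompt". The SAP does not mention the bundle, feedback reports, education or site visits.

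**Arm 2 in the protocol.** The Brief Overview says that hospital units were randomized "into either routine care (46 hospital units) or to the intervention arm (46 hospital units"), the latter receiving the "INSPIRE Stewardship Bundle which includes CPOE smart prompts, clinician feedback reports, and activities to support CPOE adoption". The Protocol Summary numbers the CPOE alert as the first component and continues: "2) clinician feedback reports, and (3) activities to support CPOE adoption (including education and alignment of CPOE workflows". It adds that these sites will "receive educational materials, participate in monthly coaching calls and every other month check in calls, and receive clinician audit reports". Section E.2.1 adds investigator site visits to Arm 2 facilities. Section G.3 defines trial success as the relative reduction in ES-DOT for the bundle arm against the routine care arm, accounting for baseline.

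**The concern.** The illustrative sentence tells the reader what a positive primary result will mean. It names one component of a multi-component intervention, and the SAP's description of Arm 2 names the same one. Someone working from the SAP would take this for a trial of prompt software against no prompt software.

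What is at stake is the interpretation. If the report follows the sentence, it will attribute to the prompts an effect that was estimated for prompts together with feedback, education and workflow support. A health system could then install the software, leave out the rest, and believe that randomized evidence supports doing so. This trial would not have supplied that evidence.

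**Working it through.** No stated sample size, alpha or margin is in dispute, so the check is whether β3 can carry the attribution.

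**Step 1. What differs between the arms.** Setting the protocol sections side by side:

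| Element | Arm 1 | Arm 2 | Where |
|---|---|---|---|
| Patient-specific risk prompts | no | yes | Brief Overview; E.2.1 |
| Clinician feedback and audit reports | no | yes | Protocol Summary; E.2.2 |
| Prompt-related education and workflow alignment | no | yes | Protocol Summary |
| Investigator site visits | no | yes | E.2.1 |
| Coaching calls | yes | yes (content differs by arm) | Protocol Summary; E.1; E.2.1 |
| Modified indication screens | yes | yes | E.2.1 |
| Toolkit | yes | yes (content differs by arm) | E.1; E.2.1 |

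Several elements other than the prompts are present only in Arm 2. Coaching calls as such are not among them.

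**Step 2. What β3 estimates.** Let A = 1 in the intervention arm and T = 1 in the intervention period. The fixed part of the model has the columns 1, A, T and A×T. Suppose the prompts and the other Arm 2 components each had their own indicator. Both are switched on only when A×T = 1, so the columns become

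1, A, T, A×T (prompts), A×T (other components).

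That is 5 columns of rank 4. The last two are identical, so only the sum of their effects can be estimated, and that sum is β3.

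**Step 3. Illustration at the planning effect.** The power section assumes an overall 12.5% relative reduction, obtained by drawing multipliers uniformly between 0.75 and 1. Their mean is (0.75 + 1)/2 = 0.875, and 1 − 0.875 = 12.5%, which reproduces the stated figure. Take 0.875 as the total rate ratio, so β3 = ln(0.875) = −0.1335. If the component effects multiply (an assumption made only for illustration), then

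β3 = ln(RR prompts) + ln(RR other), with RR other = 0.875 / RR prompts.

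| RR prompts (assumed) | RR other components | β3 |
|---|---|---|
| 0.875 | 1.000 | −0.1335 |
| 0.900 | 0.972 | −0.1335 |
| 0.950 | 0.921 | −0.1335 |
| 1.000 | 0.875 | −0.1335 |

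The estimate is the same in every row. In the last row the prompts do nothing, yet the illustrative sentence would still credit them. The table shows only that the split cannot be identified; it does not say that any row is likely.

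**Step 4. Whether another planned analysis separates the components.** The as-treated and covariate-adjusted models are the only further analyses of the primary outcome that both documents describe, and the protocol adds an intervention-period comparison by arm. None is described as isolating the prompts.

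**The case against.** The strongest reply is that this is loose shorthand and not an error in the analysis. Much of it stands.

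- The sentence opens as an example. The rule itself is the significance of β3, which both documents define as the effect of being in the intervention arm. That definition is right for the package.
- Neither document says that the prompts act alone.
- Protocol G.3 already states the correct contrast, and the Protocol Summary frames the question as a risk calculator together with audit and feedback.
- Much of the rest of the bundle serves to deliver the prompt: the adoption activities support CPOE uptake, and most of the feedback reports in E.2.2 concern acceptance, override or firing of the prompt. The prompts may well be the main active component.

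Two things do not follow. First, supporting the prompt is not the same as being the prompt. A site that installed only the software would lack that support, and one report in E.2.2 credits clinicians for standard-spectrum choices that never set off a prompt, so the feedback also reaches prescribing outside it. Second, G.3 does not cure the wording. It shows that the protocol disagrees with its own H.3 and with the SAP, and the shorthand sits in the passages that put a positive result into words.

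A reader might go further and infer that the success rule is invalid, or that a system using only the software could not obtain the estimated effect. The documents support neither. The test is sound for what was randomized, and because the prompts' share is unidentified, a prompt-only programme might achieve all, some or none of the effect. The trial simply would not show which.

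**Conclusion.** The point holds as a mismatch between the stated conclusion and the randomized contrast. The illustrative sentence in the SAP's Primary Statistical Analysis and protocol H.3, together with the SAP's prompt-only description of Arm 2, contradicts the Brief Overview, the Protocol Summary and G.3. A significant negative β3 would support a benefit of the INSPIRE Stewardship Bundle over routine care. It would not show that the prompts by themselves produced it.

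No size can be given for the misattribution, because any division of the effect fits the same β3. This conclusion rests only on the two-arm allocation and on Arm 2 receiving components besides the prompts, both stated in the protocol. It does not depend on the power figure, which comes from a bootstrap of data that the documents do not contain. The wording should be changed before results are reported; the validity of the primary test is not in question.

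**What to change.** In the illustrative sentence of the SAP (Primary Statistical Analysis) and of protocol H.3, replace the reference to the smart prompts with *the INSPIRE Stewardship Bundle*. In the SAP Background and list of arms, describe Arm 2 as the protocol does: prompts, clinician feedback reports, and adoption activities including education and workflow alignment, with success judged as in G.3. Do not list coaching calls as such as unique to Arm 2.

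The cost is a few lines of text and a slightly less specific claim. The data, model, alpha, effect estimate and power are unaffected.

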Facility Recruitment																				
Randomization with Baseline Characteristics																				
Committee Approvals																				
Coaching Calls																				
Site Visits																				
Distribute Toolkit																				
Phase in (5-month)																				
Intervention (12-month)																				
Clinician Feedback Reports																				

G. Assessment of Outcome Measures

G.1. Data Sources and Collection

Trial data will not be collected by participating sites. Instead, all variables and outcomes will be obtained from custom extractions from the HCA Healthcare computerized data warehouse. HCA Healthcare has a long-established corporate data warehouse with admission data, demographics, diagnostic and procedure codes, CPOE data, and laboratory and pharmacy data. Trial data from the computerized data warehouse will include demographic, insurer, comorbidity, and laboratory (including microbiology) data for ABD infection cohorts.

G.2. Specifications of the Appropriate Outcome Measures

The primary, secondary and safety trial outcomes are summarized below in Table 3.

G.3. Primary Outcome Measures

The primary trial outcome for ABD infections reflects the national metric of days of therapy (DOT) of extended-spectrum antibiotic use (ES-DOT), which we will evaluate for the empiric period (hospital day 1-3). Trial success will be based upon the relative reduction in this metric between the INSPIRE Stewardship Bundle vs routine care arm when accounting for baseline values.

G.4. Secondary Outcome Measures

There will be two secondary outcomes for ABD infection (antipseudomonal DOT and vancomycin DOT).

G.5. Safety Outcomes

Two safety outcomes will also be assessed. We will evaluate if increased use of standard-spectrum antibiotics causes increased ICU transfers or hospital length-of-stay.

Table 3. Trial Outcomes

Outcome	Metric for ABD Cohort
Primary Trial Outcome: Total Empiric Extended-Spectrum Antibiotic Days of Therapy (ES-DOT)	The number of different extended-spectrum antibiotics each empiric day, summed across the first 3 days of hospitalization. ¹
Secondary Trial Outcomes: Vancomycin Days of Therapy across Empiric Day and Total Empiric Antipseudomonal Antibiotic Days of	The number of days Vancomycin was received on the first 3 days of hospitalization. ¹
	The number of different antipseudomonal antibiotics each empiric day, summed

Therapy (ES-DOT)	across the first 3 days of hospitalization. ^{1,2}

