Power assessment proceeded as follows, using a Monte Carlo approach.²⁵ We used available data to define a baseline period of 1/1/2019-12/31/2019. In a bootstrap procedure, individuals were selected with replacement from within each hospital, once to represent baseline data and separately to represent “intervention period” data. Hospitals were then “randomized” to intervention or control according to multiple parameters, including number of admissions with abdominal infection and ES-DOT. We then modified the outcomes for the bootstrapped individuals in the “intervention” period in the “intervention” arm to reflect the effect of the intervention.²⁹

We assessed power to identify an overall 12.5% relative reduction in ES-DOT. This effect was implemented by reducing the relative empiric days of therapy for each admission which was exposed to the CPOE prompt. The amount of reduction was a uniform random variate between 0.75 and 1. For example, if the bootstrapped patient initially received 8 ES-DOT and was assigned to have a 12.5% reduction, then that admission intervention ES-DOT would be reduced to 7 days ($8*0.875=7$). The reduction of ES-DOT was selected with a lower bound determined by the investigators as the minimal effect achieved that would be clinically meaningful. Using this method, we have $\geq 99.9\%$ (99.6-99.9%) power to detect this effect.

Since adoption of the intervention will be heavily influenced by the ability to demonstrate safety, our study size was based on the power to detect non-inferiority for safety outcomes. We used methods similar to the above to calculate the power to identify at least a one day increase in length-of-stay for 12.5% of patients who had hospitalizations less than 14 days and found the power was 91.5% (CI 89.6-93.2%), where non-inferiority is defined as a hazard ratio no smaller than 0.98. For days to ICU transfer, we estimated the power to detect a 2% increase in transfers to the ICU on hospital day 3 through 14 to be $>99.9\%$ (CI 99.6-99.9%), where non-inferiority is defined as having a hazard ratio no greater than 1.1 (fewer days to ICU results in a hazard ratio above 1).

For completeness, we note that there are other pre-specified outcomes intended for exploratory analysis in secondary papers for the INSPIRE ABD trial in Table 4 below.

Table 4: Secondary Manuscripts - Other Pre-Specified Outcomes

Secondary Manuscripts (other pre-specified secondary exploratory analyses for later manuscripts)	

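### The flat 0.025 split for the two secondary outcomes is valid, but Holm's procedure gives the same 5% familywise error with never less power

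*SAP*

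**What the plan says.** The SAP (Primary Statistical Analysis) and the protocol (H.3, Primary Statistical Analysis) use the same rule. For ES-DOT: "The primary trial analysis will use an as-randomized unadjusted model with two-tailed significance set at alpha = 0.05". For the two secondary outcomes, vancomycin DOT and antipseudomonal DOT: "adjustment for multiple comparisons with two-tailed significance set at alpha = 0.025 for the two secondary outcomes". The text does not say that 0.025 applies to each outcome, but half of 0.05 is the natural reading.

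Neither document describes a step-down rule, a testing order, recycling of alpha, or what becomes of the secondary tests if ES-DOT is not significant.

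On success, the SAP says: "The assessment of trial success will be determined by assessing the significance of the arm by period interaction term". The surrounding text interprets that term as a relative rate of ES-DOT, and protocol section G.3 likewise bases success on the primary metric.

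On power, the protocol (Power Size/Sample Size Calculations) says: "We assessed power to identify an overall 12.5% relative reduction in ES-DOT". The result is at least 99.9%, with an interval of 99.6 to 99.9%. No effect size, variance or power is given for either secondary outcome.

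**The concern.** A fixed 0.025 for each of two tests is the simplest way to hold the pair at 5%, but not the most efficient. When one of the two nulls has been rejected at 0.025, only one remains in the family. It can be tested at the full 0.05 without exceeding 5% overall. The flat split never uses that allowance. What is at stake is power for whichever secondary outcome has the weaker signal: a p-value between 0.025 and 0.05 would be declared non-significant for no gain in error control.

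A smaller, separate point is that the plan does not say how a significant secondary result would be described if ES-DOT were not significant. Under SAP Table 2 both secondary outcomes count drugs that also count toward ES-DOT, so a reader could be unsure how to take such a result.

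**Working it through.** **Inputs from the documents.** Primary two-sided alpha 0.05; secondary two-sided alpha 0.025; two secondary outcomes; stated ES-DOT power of at least 99.9% (interval 99.6 to 99.9%) for a 12.5% reduction; 46 hospital units per arm. **Assumed:** power of each secondary outcome, and correlations between tests.

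**1. Reproducing the plan's figure.** Bonferroni: 0.05/2 = 0.025, an exact match. The Šidák level, 1 − √0.95 = 0.0253, does not match.

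**2. Error within the secondary pair.** The bound is 2 × 0.025 = 0.05. If the tests are independent, it is 1 − 0.975² = 0.0494. The pair is controlled.

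**3. Cost of testing one outcome at 0.025 instead of 0.05.** The critical values are 2.241 and 1.960. If power at 0.05 is p, power at 0.025 is Φ(1.960 + z_p − 2.241).

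| Power at 0.05 | Power at 0.025 | Difference (points) |
|---|---|---|
| 50% | 38.9% | 11.1 |
| 70% | 59.6% | 10.4 |
| 80% | 71.2% | 8.8 |
| 90% | 84.1% | 5.9 |
| 99.9% | 99.75% | 0.15 |

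**4. What Holm recovers.** Holm restores the difference only when the other outcome passes 0.025. With independent tests:

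power under Holm = power at 0.025 + (difference) × (other outcome's power at 0.025).

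Take the other outcome to have 90% power at 0.05, hence 84.1% at 0.025:

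- weaker outcome 50%: 38.9 + 11.1 × 0.841 = 48.2%, gain 9.3 points
- 70%: 59.6 + 10.4 × 0.841 = 68.3%, gain 8.7 points
- 80%: 71.2 + 8.8 × 0.841 = 78.6%, gain 7.4 points
- 90%: 84.1 + 5.9 × 0.841 = 89.1%, gain 5.0 points

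Simulation with a correlation of 0.3 between the two tests changes these gains by about half a point or less.

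**5. If both outcomes have power near that stated for ES-DOT.** At 99.9% each, the gain is 0.15 × 0.9975, or about 0.15 points. At 99.6% each (the lower limit of the protocol's interval), power at 0.025 is 99.1% and the gain is about 0.5 points.

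**6. The same range on a variance scale.** Take SE = s × √(2/46) and effect −log(0.875) = 0.1335, where s is the between-hospital SD of the log change. Stated ES-DOT power of 99.9% to 99.6% corresponds to s of about 0.13 to 0.14. Assumed values of 0.20, 0.25 and 0.30 give power at 0.025 versus 0.05 of 83% versus 89%, 63% versus 73%, and 46% versus 57%. Those differences of 6 to 11 points are maxima, because they take the other secondary outcome as already significant.

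**7. All three tests together, for the optional point.** If all three nulls are true and nothing links the secondary tests to the primary, the bound is 0.05 + 0.05 = 0.10. With independence the error is 1 − 0.95 × 0.975² = 0.097. Simulation (2 million draws) gives about 0.093 to 0.094, 0.088 to 0.089, 0.079 and 0.072 for primary–secondary correlations of 0.3, 0.5, 0.7 and 0.8. Testing the secondary outcomes only after a significant primary would hold it at 0.05.

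**The case against.** The plan recognises multiplicity and controls it within the secondary family. Controlling the primary and the secondary family separately is an accepted choice. That stands: nothing here shows a wrong alpha.

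A reader might infer something stronger, that secondary claims could stand in for a failed primary and that the plan's error rate is therefore close to 10%. The documents do not support this. They tie success to the ES-DOT interaction term, never call the secondary outcomes confirmatory, and never declare a three-test family. The 7 to 10% figure arises only if all three nulls are true. The upper end needs independent tests, which is unlikely when the secondary outcomes share drugs with the primary. If the ES-DOT effect is real, error over the two secondary tests is at most 5% with or without a gate.

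A reader might also infer that the split costs 6 to 11 points of power, mainly on vancomycin. That is not supported either. It needs hospital SDs of 0.20 to 0.30, which give only 57 to 89% power at 0.05 for a 12.5% reduction, far from the figure stated for ES-DOT. A secondary outcome could be more variable or respond less, but the documents give no usage, variance or effect for either, and nothing shows which is weaker. Nor does the missing link to the primary waste power; a gate can only lower it for the secondary outcomes.

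Two practical objections also stand. The SAP is dated 3/29/2024, after the intervention period, so relaxing a threshold now needs care. And Bonferroni has simple matching 97.5% intervals, whereas Holm has no equally simple simultaneous ones.

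**Conclusion.** The flat split is valid but inefficient. Holm has the same 5% familywise error under any dependence and never less power, so the change is an improvement in principle whatever the data look like.

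Its size is uncertain. It is about 5 to 9 points for the weaker outcome if that outcome has 50 to 90% power at 0.05 and the other has 90%, and under 1 point if both are close to the power stated for ES-DOT. Both ranges rest on assumed secondary power and a normal approximation; the protocol's bootstrap data are not available to narrow them.

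The lack of a statement about secondary results after a non-significant primary is a gap in reporting rules on which reasonable statisticians differ. It is not an error. This is a low-cost refinement, and the validity of the primary analysis does not depend on it.

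**What to change.** In both the SAP and the protocol, replace the clause on the secondary significance level with:

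> The two secondary outcomes are tested by Holm at overall two-sided 0.05: the smaller p-value against 0.025 and, if significant, the larger against 0.05.

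Date the change and make it before comparative results are seen. If that is no longer possible, keep the flat split and write that 0.025 applies to each outcome.

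Optionally, add that secondary results are descriptive if ES-DOT is not significant. If the stated ES-DOT power is right, this costs about 0.1 point of secondary power.

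The cost is one sentence in each of two documents and the loss of simple simultaneous intervals that match the tests. The 97.5% intervals can still be reported.
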